3.2.2 Rationale for Study Population

Nirsevimab has the potential to address a serious unmet medical need by protecting all infants from RSV disease with once-per-season dosing. Palivizumab is not licensed in China and currently there are no other options available for the prevention of RSV disease. This Phase 1 adult study is designed to assess the PK, ADA, safety, and tolerability of a single IM dose of nirsevimab in healthy Chinese adult subjects to support the registration of nirsevimab in China. The PK profile of nirsevimab assessed after dose administration in Chinese adult subjects will be compared to global adult subjects with different racial and ethnic backgrounds.

3.2.3 Rationale for Endpoints

Serum concentration of nirsevimab at selected time points will be evaluated as the primary endpoint to confirm that adequate serum exposures are maintained at least 5 months after dosing (ie, through Day 151; duration of a typical RSV season). The estimated PK parameters from the adult Chinese subjects in this study will be compared for similarity with those obtained from non-Chinese adult subjects from the global Phase 1a Study D5290C00001.

Nirsevimab being a mAb with a half-life extending YTE modification has a predictable linear PK profile across a range of doses studied both in adults and infants. Also, it does not have any internal targets; thus, it does not go through any target-mediated clearances to have the potential to alter the PK profile past the 150 days from the injection. Therefore, the 150-day PK profile comparison based on only C_{max} , t_{max} , and AUC_{0-150} assures the similarity of efficacious exposures as well as provides the opportunity to confirm the safety.

ADA will be measured at selected time points throughout the study up to Day 151.

Safety endpoints include TEAEs, TESAEs, AESIs (defined as hypersensitivity including anaphylaxis, immune complex disease, and thrombocytopenia), and NOCDs.

4 MATERIALS AND METHODS

4.1 Subjects

4.1.1 Number of Subjects

A total of approximately 24 subjects will be randomized to receive a single IM dose of either nirsevimab (n = 18) or placebo (n = 6).

4.1.2 Inclusion Criteria

Subjects must meet all of the following criteria:

- 1 Age 18 to 45 years, inclusive, at the time of screening.

- 2 Written informed consent and any locally required authorization obtained from the subject prior to performing any protocol-related procedures, including screening evaluations.
- 3 Females of childbearing potential who are sexually active with a nonsterilized male partner must have used at least 1 highly effective method of contraception (see [Appendix A](#) for definition of females of childbearing potential and for a description of highly effective methods of contraception) from screening and must agree to continue using such precautions for 150 days after receipt of the dose of investigational product. It is strongly recommended for the male partner of a female subject to also use a male condom plus spermicide throughout this period. Cessation of contraception after this point should be discussed with a responsible physician. Periodic abstinence, the rhythm method, and the withdrawal method are not acceptable methods of contraception.
 - (a) Females not of childbearing potential who are either permanently sterilized (hysterectomy, bilateral oophorectomy, or bilateral salpingectomy) or postmenopausal. Women < 50 years of age will be considered postmenopausal if they have been amenorrheic for ≥ 12 months prior to the planned date of randomization without an alternative medical cause and have follicle-stimulating hormone levels in the postmenopausal range.
- 4 Nonsterilized male subjects who are sexually active with a female partner of childbearing potential must use a male condom with spermicide from Day 1 (the day of investigational product administration) through 150 days after receipt of the dose of investigational product. It is strongly recommended for the female partner of a male subject to also use a highly effective method of contraception throughout this period, as described in [Appendix A](#). In addition, male subjects must refrain from sperm donation while on study and for 150 days after the final dose of investigational product.
- 5 Weight ≥ 45 kg and ≤ 110 kg and body mass index of 19 to 26 kg/m² at screening.
- 6 Healthy Chinese subjects (both male and female) based on medical history, physical examination, vital signs, and laboratory tests, as determined by the Investigator.
- 7 Normotensive (defined as systolic blood pressure < 140 mm Hg and diastolic blood pressure < 90 mm Hg).
- 8 Normal electrocardiogram (ECG) as judged by the Investigator at screening (within 28 days prior to Day 1).
- 9 Ability to complete the follow-up period of 150 days following administration of investigational product as required by the protocol.

4.1.3 Exclusion Criteria

Any of the following would exclude the subject from participation in the study:

- 1 Acute illness at study entry (pre-dose on Day 1). If, in the opinion of the Investigator, the illness is transient and of no medical importance, it would be permissible to reassess the subject for study and dosing eligibility after resolution as long as it is within the overall 28-day study screening period.
- 2 Fever $\geq 99.5^{\circ}\text{F}$ (37.5°C) on day of dosing.

- 3 Any drug therapy within 14 days prior to Day 1 (except contraceptives). If, in the opinion of the Investigator, the medication was taken for a transient illness that has resolved, it would be permissible to reassess the subject for study and dosing eligibility after resolution as long as it is within the overall 28-day study screening period.
- 4 Blood donation or in any other way had a loss of blood in excess of 400 mL within 6 months prior to study entry.
- 5 Receipt of immunoglobulin or blood products within 6 months prior to study entry.
- 6 Receipt of any investigational drug therapy within 120 days prior to investigational product dosing or planned to receive any investigational drug therapy within 150 days after investigational product dosing.
- 7 Receipt of any live vaccine within 30 days and other vaccines within 14 days prior to investigational product dosing.
- 8 Previous receipt of any marketed or investigational mAb.
- 9 Previous vaccination against RSV.
- 10 History of immunodeficiency or receipt of immunosuppressive medications during the prior year.
- 11 History of allergic disease or reactions likely to be exacerbated by any component of the investigational product or a history of drug or other allergy that, in the opinion of the investigator, contraindicates their participation.
- 12 History of asthma.
- 13 History of autoimmune disorder.
- 14 Previous medical history or evidence of an intercurrent illness that, in the Investigator's opinion, may compromise the safety of the subject in the study.
- 15 Evidence of any systemic disease on physical examination.
- 16 Evidence of infection (ie, positive laboratory test result) with hepatitis A, B, or C virus, syphilis, or human immunodeficiency virus.
- 17 Any of the following laboratory assessments at screening (must be within 28 days before study entry):
 - (a) Hemoglobin < 120 g/L for males and < 110 g/L for females
 - (b) White blood cell count < $3.5 \times 10^9/L$
 - (c) Platelet count < $120 \times 10^9/L$
 - (d) Aspartate aminotransferase (AST), alanine aminotransferase (ALT), urea, serum creatinine > upper limit of normal (ULN)
 - (e) Urine Class A drug screen positive for amphetamines, opiates, or cocaine
 - (f) Other abnormal laboratory values in the screening panel, which in the opinion of the Investigator, are judged to be clinically significant; other abnormal laboratory values in the screening panel which, in the opinion of the Investigator, are judged to potentially confound analysis of study results
- 18 Pregnant or nursing mother. All female subjects will be screened to rule out pregnancy prior to enrollment using serum beta human chorionic gonadotropin (β hCG) testing.

- 19 Active alcohol or drug abuse or history of alcohol or drug abuse that, in the opinion of the Investigator, might compromise subject safety, study safety assessments, or ability of the subject to comply with study requirements.
- 20 Any condition that, in the opinion of the Investigator, would interfere with evaluation of the investigational product or interpretation of subject safety or study results.
- 21 Concurrent enrollment in another interventional study.
- 22 Employees of the Sponsor, clinical study site, or any other individuals involved with the conduct of the study, or immediate family members of such individuals.

4.1.4 Subject Enrollment and Randomization

Study participation begins (ie, a subject is “enrolled”) once written informed consent is obtained. Once informed consent is obtained, a subject identification (SID) number will be assigned by a central system (eg, an interactive web response system [IWRS]), and the screening evaluations may begin to assess study eligibility (inclusion/exclusion) criteria. The SID number will be used to identify the subject during the screening process and throughout study participation, if applicable.

A master log of all consented subjects will be maintained at the site and will document all screening failures (ie, subjects who are consented but do not meet study eligibility criteria and/or are not randomized), including the reason(s) for screening failure.

Subjects who fail to meet the inclusion/exclusion criteria (ie, screening failures) should not be randomized (if applicable) or receive investigational product. Rescreening is not permitted.

4.1.5 Withdrawal from the Study

Subjects are free to withdraw their consent to participate in the study at any time, without prejudice to further treatment. Subjects who withdraw consent will be asked about the reason(s) and the presence of any AEs. If the subject is willing, the subject will be seen and assessed by the Investigator. AEs will be followed up. If a subject withdraws from further participation in the study, then no further study visits or data collection should take place. The reason for withdrawal must be recorded in the eCRF.

Subjects who have received investigational product will be followed for protocol-specified assessments including follow-up of any AEs unless consent is withdrawn from further study participation or the subject is lost to follow-up (Section 4.1.7).

4.1.6 Discontinuation of Investigational Product

Not applicable as each subject will receive a single dose of investigational product.

4.1.7 Lost to Follow-up

A subject will be considered potentially lost to follow-up if he or she fails to return for scheduled visits and is unable to be contacted by the study site.

To prevent the subject from being lost to follow-up, it is recommended that the study sites maintain up-to-date contact details for subjects, including next of kin or other emergency contacts (if allowed by national regulation).

The Investigator should educate the subject on the importance of maintaining contact with the Investigator/study site throughout the study.

The following actions must be taken if a subject fails to return to the site for required study visits:

- The site must attempt to contact the subject and reschedule the missed visit as soon as possible and counsel the subject on the importance of maintaining the assigned visit schedule.
- Repeated attempts must be made to regain contact with the subject or next of kin/emergency contact by repeat telephone calls, emails, and/or certified letter. These contact attempts should be documented in the subject's medical record.

Efforts to reach the subject should continue until the end of the study.

The subject will be classified as lost to follow-up only if he/she has failed to return for the required study visits and his/her vital status remains unknown at the end of the study, despite all above listed efforts.

4.1.8 Replacement of Subjects

Subjects will not be replaced.

4.1.9 Withdrawal of Informed Consent for Data and Biological Samples

The Sponsor ensures that biological samples are returned to the source or destroyed at the end of a specified period as described in the informed consent.

If a subject withdraws consent for further study participation, any samples collected prior to that time may still be given to and used by the Sponsor but no new data or samples will be collected unless specifically required to monitor safety of the subject.

If a subject withdraws consent to the use of donated biological samples, the samples will be disposed of/destroyed, and the action documented. If samples are already analyzed, the Sponsor is not obliged to destroy the results of this research.

The Principal Investigator:

- Ensures subjects' withdrawal of informed consent to the use of donated samples is notified immediately to the Sponsor.
- Ensures that biological samples from that subject, if stored at the study site, are immediately identified, disposed of/destroyed, and the action documented.
- Ensures the organization(s) holding the samples is/are informed about the withdrawn consent immediately and that samples are disposed of/destroyed, the action documented, and the signed document returned to the study site.
- Ensures that the subject and the Sponsor are informed about the sample disposal.

The Sponsor ensures the organization(s) holding the samples is/are informed about the withdrawn consent immediately and that samples are disposed of/destroyed and the action documented and returned to the study site.

4.2 Schedule of Study Procedures

4.2.1 Enrollment/Screening Period

Table 4 shows all procedures to be conducted at the screening visit. Assessments should be performed in the order shown in the table.

Table 4 Schedule of Screening Procedures

Study Period Procedure / Study Day or Week	Screening	
	Day -28 to Day -2	Day -1
Written informed consent/ assignment of SID number	X	
Medical history	X	X ^a
Physical examination (complete)	X	X ^a
Height, weight	X	
Electrocardiogram (ECG)	X	X
Vital signs	X	X
Serum chemistry ^b	X	X
Hematology ^b	X	X
Urinalysis ^b	X	X
Pregnancy test ^c	X	X
FSH ^d	X	
Hepatitis A, B, C; HIV; Syphilis	X	
Urine Class A drug screen ^b	X	X
Assessment of AEs/SAEs	X	X
Concomitant medications	X	X
Verify eligibility criteria	X	X

Table 4 Schedule of Screening Procedures

Study Period	Screening	
Procedure / Study Day or Week	Day -28 to Day -2	Day -1
Admission		X

ADA = antidrug antibody; AE = adverse event; β hCG = beta human chorionic gonadotropin; FSH = follicle-stimulating hormone; HIV = human immunodeficiency virus; PK = pharmacokinetics; SAE = serious adverse event; SID = subject identification.

- ^a Update screening medical history and complete physical examination (any new findings since screening).
- ^b Screening serum chemistry and hematology assessments reviewed and found to be within normal limits by the Site Investigator. Serum chemistry assessments should be collected under fasting conditions (fasting starts 8 hours before sample collection). If serum chemistry, hematology, urinalysis and urine class A drug screen assessments at screening visit (Day -28 to Day -2) are performed within 7 days of randomization, the assessments at Day -1 can be omitted.
- ^c Female subjects only. Serum pregnancy test will be performed at screening visit (Day -28 to Day -2). Urine pregnancy test will be performed on Day -1 to confirm eligibility. Pregnancy test must be negative prior to dosing.
- ^d FSH will be tested only in women < 50 years of age who have been amenorrheic for \geq 12 months.

4.2.2 Treatment and Follow-up Periods

Investigational product is administered on Day 1. Table 5 and Table 6 show all procedures to be conducted on Day 1 and during the post-dose follow-up period, respectively.

Table 5 Schedule of Treatment Period Procedures

Procedure	Investigational Product Administration: Day 1			
	Pre-dose	Dosing	Post-dose	
			30 min post (\pm 5 min)	60 min post (\pm 5 min)
Abbreviated Physical examination	X			
Vital signs ^a	X		X	X
Blood sample for PK, ADA	X			
Assessment of AEs/SAEs	X	X	X	X
Assessment of AESIs and NOCDs		X	X	X
Concomitant medications	X			
Randomization ^b	X			
Investigational product administration		X		

ADA = antidrug antibody; AE = adverse event; AESI = adverse event of special interest; IM = intramuscular; NOCD = new onset chronic disease; PK = pharmacokinetic; SAE = serious adverse event.

- ^a Vital signs will be monitored before and after IM administration of investigational product. Two pre-dose (within 60 minutes prior to dosing) blood pressure and heart rate readings should be obtained 5 minutes apart. Vital signs should be monitored within 60 minutes prior to dosing, and 30 and 60 (\pm 5 minutes) minutes after the administration of the investigational product.
- ^b Randomization should occur before blood sampling.

Table 6 Schedule of Follow-up Period Procedures

Procedure	Post-dose Follow-up: Day (\pm Assessment Window [day])							
	2	4	6	8	15 (\pm 1d)	31 (\pm 2d)	91 (\pm 5d)	151 (\pm 10d)
Physical examination ^a	X		X		X	X	X	X
Vital signs	X		X		X	X	X	X
Serum chemistry			X		X	X	X	
Hematology			X		X	X	X	
Urinalysis			X		X	X	X	
PK blood sample	X (\pm 2h)	X (\pm 3h)	X (\pm 3h)	X (\pm 3h)	X	X	X	X
ADA blood sample						X	X	X
Assessment of AEs/SAEs	X	X	X	X	X	X	X	X
Assessment of AESIs and NOCDs	X	X	X	X	X	X	X	X
Concomitant medications	X	X	X	X	X	X	X	X
Discharge	X							

ADA = antidrug antibody; AE = adverse event; AESI = adverse event of special interest; d = day; h = hour; NOCD = new onset chronic disease; PK = pharmacokinetic; SAE = serious adverse event.

^a Abbreviated physical examinations will be performed at Day 2, Day 6, Day 15, Day 31 and Day 91. A complete physical examination should be performed on Day 151.

4.3 Description of Study Procedures

4.3.1 Medical History, Physical Examination, Height, Weight, Vital Signs and Electrocardiogram

A complete medical history will be obtained at screening and a medical history update (for any new findings since screening) will be obtained on Day -1.

A complete physical examination will be performed at screening visit (Day -28 to Day -2), Day -1 (updated with any new findings since screening), and Day 151, and it will include an assessment of the following: general appearance, respiratory, cardiovascular, abdomen, skin, head and neck (including ears, eyes, nose and throat), lymph nodes, thyroid, musculoskeletal (including spine and extremities) and neurological systems. An abbreviated physical examination will be performed at all other study visits, and it will include an assessment of general appearance, abdomen, cardiovascular, and respiratory systems. The height and/or weight will be performed as noted in [Table 4](#).

Vital signs (temperature, blood pressure, respiratory rate, and heart rate measurements) will be collected at screening visit (Day -28 to Day -2), Day -1 and on Day 1 as defined in [Table 4](#) and [Table 5](#). Refer to [Table 6](#) for the timings of assessments during the follow-up period.

At Screening, 12-lead ECG will be obtained after 5 minutes supine rest and prior to blood draw. Skin must be cleaned, and electrodes should be positioned according to standard 12-lead ECG placement. All 12-lead ECGs will be recorded and evaluated by the Investigator. The Investigator will judge the overall interpretation as normal or abnormal. If abnormal, it will be decided whether the abnormality is clinically significant or not. The reason for the abnormality will be recorded in the eCRF. These ECGs will be documented in the eCRF by recording date, time, heart rate, overall assessment as normal and abnormal, and whether the abnormality is clinically significant or not.

All ECGs will be documented by recording date, time of collection, heart rate, PR, RR, QRS, and QT intervals from the 12-lead ECG.

If indicated additional 12-lead ECG assessments can be made at the discretion of the Investigator. These assessments should be entered as an unscheduled assessment in the appropriate eCRF.

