The safety profile of nirsevimab was comparable to that of placebo, with no identified risks. Overall, 86.2% of subjects in the nirsevimab group and 86.8% of subjects in the placebo group had at least 1 TEAE. TEAEs \leq 1 day post dose occurred in 2.5% of subjects in both groups. In comparison to the placebo group, the nirsevimab group had a lower incidence of TEAEs occurring \leq 7 days post dose (nirsevimab 12.5%, placebo 15.2%), TEAEs \geq Grade 3 in severity (nirsevimab 8.0%, placebo 12.5%), or TESAEs (nirsevimab 11.2%, placebo 16.9%). The majority of the TEAEs were mild or moderate in severity. The most common TESAEs, based on the nirsevimab group, were bronchiolitis (2.1% nirsevimab, 4.4% placebo), LRTI (1.4% nirsevimab, 2.7% placebo), bronchitis (1.4% nirsevimab, 2.3% placebo), and pneumonia (1.3% nirsevimab, 2.1% placebo). None of the TESAEs were considered related to investigational product by the Investigator. Five deaths were reported during the study through Day 361, including 2 subjects (0.2%) in the nirsevimab group and 3 subjects (0.6%) in the placebo group. None of the deaths were related to investigational product according to the Investigator.

Overall, the incidence of treatment-related TEAEs (nirsevimab 2.3%, placebo 2.1%); AESIs, including hypersensitivity, immune complex disease, and thrombocytopenia (nirsevimab 0.5%, placebo 0.6%); and NOCDs (nirsevimab 0.4%, placebo 0.8%) was low and generally comparable between the placebo and nirsevimab groups. AESIs were reported in 5 subjects

(4 subjects with rash or rash macular and 1 subject with petechiae) in the nirsevimab and 3 subjects (rash or rash papular) in the placebo group. All events were Grade 1 in severity. The TEAE of petechiae that was reported as an AESI was 1 day in duration and was reported by the Site Investigator based on description by the parent. There were no laboratory assessments for the petechiae.

TEAEs that involved the skin and subcutaneous tissues (including diaper rash) were collected as skin reactions, with a few exceptions for skin reactions that could be definitively diagnosed such as impetigo, varicella, and scabies. Skin reactions were reported in a similar percentage of subjects in both treatment groups (nirsevimab 32.9%, placebo 30.9%).

Pharmacokinetics

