1.6 Benefit-Risk and Ethical Assessment

The study will be performed in accordance with ethical principles that have their origin in the Declaration of Helsinki and are consistent with International Council for Harmonisation (ICH)/Good Clinical Practice (GCP), and applicable regulatory requirements.

To evaluate the clinical benefit-risk balance for nirsevimab, nonclinical and clinical data have been taken into consideration. Based on the risk of serious RSV disease in infants and high-risk children, there is an established unmet medical need for the use of nirsevimab for prophylaxis in all infants entering their first RSV season and in high-risk- preterm infants and children ≤ 24 months of age with CLD or CHD. Benefits for nirsevimab over placebo include a clinically meaningful reduction in medically attended LRTI due to RSV in infants and expected similar benefit for high-risk children. Nirsevimab is not expected to offer benefit to the healthy Chinese adult subjects in this study. The PK, ADA, and safety results of this study will support the registration of nirsevimab in China.

Nirsevimab has no endogenous targets, and no safety concerns have been identified in nonclinical or clinical studies to date. The potential risks are based primarily on safety risks that may be observed with any immunoglobulin, including mAbs such as palivizumab. These potential risks include, but are not limited to, hypersensitivity (including anaphylaxis), immune complex disease, thrombocytopenia, and injection site reactions. To date, there have been no observed events of anaphylaxis, significant hypersensitivity reactions, immune complex disease, or thrombocytopenia attributable to nirsevimab in the clinical studies. Nonetheless, subjects in nirsevimab clinical studies will continue to be monitored for important potential risks, and routine pharmacovigilance and risk minimization activities will be performed accordingly.

The benefit-risk assessment for nirsevimab in prevention of RSV disease based on the development through Phase 2b is favorable.

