5.3.1 Anaphylaxis and Other Serious Hypersensitivity Reactions Including Immune Complex Disease

Administration of polyclonal immunoglobulin preparations and mAbs has been associated with anaphylaxis and other serious hypersensitivity reactions, including immune complex disease, that occurs during or after dosing. Anaphylaxis is a rare event, usually occurring after subsequent exposure to antigen, and it is most commonly accompanied by severe systemic skin and/or mucosal reactions. It is potentially a fatal, systemic allergic reaction that is distinct from simple allergic reactions (eg, rash, pruritus) because of the simultaneous involvement of several organ systems ([Sampson et al 2006](#)). A full definition of anaphylaxis is provided in [Appendix C](#). See Section 5.5 for recording AEs. A hypersensitivity reaction is defined as an acute onset of an illness with involvement of the skin, mucosal tissue, or both during or after administration of investigational product (but does not meet the definition of anaphylaxis) ([Pichler 2019](#)).

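### None of the five scheduled post-dose examinations before Day 151 requires a look at the skin, and no visit schedules an injection-site inspection (minor; cheap to mend)

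*Supplement*

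**What the plan says.** Section 4.3.1 describes two examinations. The complete one lists the skin as an item of its own: "general appearance, respiratory, cardiovascular, abdomen, skin, head and neck", followed by further systems. It is done at screening, on Day -1 and on Day 151. The abbreviated one is narrower: "it will include an assessment of general appearance, abdomen, cardiovascular, and respiratory systems". Neither list names the injection sites.

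Footnote a of Table 6 (section 4.2.2) assigns the two types to visits: "Abbreviated physical examinations will be performed at Day 2, Day 6, Day 15, Day 31 and Day 91", and "A complete physical examination should be performed on Day 151". On Day 1, Table 5 has an abbreviated examination before dosing only. After dosing that day it schedules vital signs and AE and AESI assessment at 30 and 60 minutes.

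Section 5.3.1 defines a hypersensitivity reaction as an "acute onset of an illness with involvement of the skin, mucosal tissue, or both". Section 1.6 gives the potential risks as including "hypersensitivity (including anaphylaxis), immune complex disease, thrombocytopenia, and injection site reactions". Under section 4.5.1.3 each subject receives three 1 mL injections, two in one deltoid and one in the other.

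**The concern.** The scheduled examination and the protocol's own safety content do not line up. Two of the potential risks named in section 1.6, hypersensitivity and injection-site reactions, show mainly on the skin, and the examination used at every marked post-dose visit before Day 151 does not require the skin to be examined. The skin baseline is recorded twice, at screening and on Day -1, but no scheduled comparison follows until the end of the study.

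TEAE and AESI occurrence are secondary endpoints (section 2.2), and section 5.5.4 makes a new, clinically relevant examination finding, compared with baseline, reportable as an AE. For skin and local reactions that route is hardly used. Whether a mild finding is recorded then depends on what the subject mentions and what staff happen to notice, not on the same look at the same sites in all 24 subjects. At stake is how completely and consistently mild skin and local reactions are recorded. The PK primary endpoint is not affected.

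**Working it through.** No plan figure has to be reproduced. The check sets examination content against the visit schedule, and then against the other routes of detection.

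**Step 1: which post-dose examinations require skin?**

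| Follow-up day | Examination in Table 6 | Skin listed in 4.3.1 | Injection sites listed |
|---|---|---|---|
| 2 | abbreviated | no | no |
| 4 | none marked | – | – |
| 6 | abbreviated | no | no |
| 8 | none marked | – | – |
| 15 | abbreviated | no | no |
| 31 | abbreviated | no | no |
| 91 | abbreviated | no | no |
| 151 | complete | yes | no |

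- Examinations after dosing: 6. Abbreviated: 5. Complete: 1.
- Before Day 151, those requiring skin: 0 of 5.
- First scheduled post-dose skin examination: Day 151, that is 150 days after dosing. With the ±10-day window the earliest is 151 − 10 = Day 141.
- Visits with a scheduled injection-site inspection: 0 of 8.

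**Step 2: is the number of examinations itself clear?** Section 4.3.1 says: "An abbreviated physical examination will be performed at all other study visits". Table 6 marks none on Days 4 and 8. Read by the text, abbreviated examinations before Day 151 would number 5 + 2 = 7. Read by the table, they number 5. The count requiring skin is 0 on either reading, so the discrepancy needs reconciling but does not change the point.

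**Step 3: what else could pick up these events?**

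- AE and AESI assessment (Tables 5 and 6): at 30 and 60 minutes and at all 8 follow-up visits. What the AESI assessment consists of is not specified.
- AE collection (5.5.3): spontaneous report, an open question, or observation.
- Subject card (5.7.4.1): six signs, of which four concern skin or mucosa (urticaria, itching, angioedema, rash) and two are respiratory. Local injection-site reactions are not among them.
- On-site stay (Tables 4 and 6): admission on Day -1, discharge on Day 2.
- Platelet counts (4.3.2, Table 6): Days 6, 15, 31 and 91. They serve the thrombocytopenia criterion in 5.7.4.2, which is a platelet count.

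**Step 4: what remains uncovered?** Thrombocytopenia has its own scheduled measurement. Hypersensitivity has the AESI assessment and the card. Local reactions have neither a scheduled inspection nor a place among the card's listed signs, and rely on the open question and on observation. For skin in general, no scheduled step before Day 151 requires an examiner to look.

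**The case against.** The strongest reply is that detection does not rest on the physical examination. AEs and AESIs are assessed at every follow-up visit, including Days 4 and 8. Events seen by staff count as well as those reported. Subjects are healthy adults with a card telling them to report urticaria or rash at once, and they are on site until Day 2. The listed items are a minimum, and assessing general appearance may catch a visible rash. This largely stands, and it is why the point is minor. It does not close the gap. The AESI assessment has no stated content, and the complete examination lists general appearance and skin separately, so the first cannot be assumed to include the second. Deltoid skin under clothing is not reliably seen unless someone is asked to look.

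Three stronger readings are tempting, and the documents do not support them.

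- *That thrombocytopenia would be missed because petechiae are not looked for.* The reporting criterion is a platelet count below 120,000 per µL, and platelets are measured on four follow-up days.
- *That the Phase 2b AESIs measure the loss.* The nirsevimab cases were "4 subjects with rash or rash macular and 1 subject with petechiae", and the three placebo cases were also rash. All were Grade 1 events in infants, who cannot report for themselves. In Phase 1a adults there were no AESIs among 102 nirsevimab recipients, 78 of them at 300 mg IM. Even at the infant rate, 5/968 = 0.52%, 18 subjects would give 18 × 0.0052 = 0.09 expected cases. Likewise 1/18 = 5.6% is only the weight of one subject and says nothing about how many events would be missed.
- *That a finding of no AESIs would be weak evidence for this reason.* With perfect detection, 0 of 18 still has an exact two-sided 95% upper limit of 1 − 0.025^(1/18) = 18.5%. Sample size sets that limit. The analysis section (4.8.4.1) also words the AESI as serious hypersensitivity, which a carded adult is unlikely to overlook.

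**Conclusion.** The point holds as a minor one. Before Day 151, 0 of 5 scheduled post-dose examinations require the skin to be examined, and 0 of 8 follow-up visits schedule an injection-site inspection, although local reactions are a named potential risk and hypersensitivity is defined mainly by skin or mucosal involvement. What is missing is systematic examiner-based ascertainment, not all detection. It is clearest for injection-site reactions, which the card's listed signs leave out.

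The documents give no basis for estimating how many events would go unrecorded, and none is offered. The conclusion rests on two assumptions: that the unspecified AESI assessment does not already require a skin inspection, and that a local reaction would usually no longer be visible at Day 151. The second is a judgement, not stated in the protocol. The difference between 4.3.1 and Table 6 over Days 4 and 8 is a separate inconsistency that stands whatever view is taken on skin.

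**What to change.** In section 4.3.1, add 'skin, including the injection sites' to the content of the abbreviated examination already scheduled on Days 2, 6, 15, 31 and 91. Findings can then be compared with the skin baseline from screening and Day -1, and section 5.5.4 already says when a new finding becomes an AE.

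Reconcile the statement in 4.3.1 that the abbreviated examination takes place at all remaining visits with Table 6 and its footnote, which have none on Days 4 and 8.

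The cost is one more item on an existing examination and its eCRF page, with no new visit, procedure or staff. The downside is that a few more mild skin or local findings will be recorded.
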